13.11. Withdrawal Due to Serious Adverse Events

When a subject withdraws due to a SAE, the SAEs must be reported in accordance with the reporting requirements defined below.

13.12. Eliciting Adverse Event Information

The Investigator is to report all directly observed AEs and all AEs spontaneously reported by the study subject. In addition, each study subject will be questioned about AEs.

13.13. Reporting Requirements

Each AE is to be assessed to determine if it meets the criteria for a SAE. If a SAE occurs, expedited reporting will follow local and international regulations, as appropriate.

For randomized subjects, all AEs will be reported on the AE source document and then entered into the EDC system. A Clinical Serious Adverse Event (SAE) Report Form must be completed if the event is considered to be serious. It should be noted that this Clinical SAE Report Form for collection of SAE information is not the same as the AE page(s) of the CRF. Where the same data are collected, the forms must be completed in a consistent manner. For example, the same AE term should be used on both forms. Adverse events should be reported using concise medical terminology on the CRFs as well as on the form for collection of SAE information.

13.14. Serious Adverse Event Reporting Requirements

If a SAE occurs, the Sponsor is to be initially notified by telephone immediately upon awareness of the event by the Investigator's site. Within 24 hours of the Investigator site's awareness of the event, the study site must send the Sponsor the Clinical SAE Report Form. This timeframe also applies to additional new information (follow-up) on previously forwarded SAE reports as well as to the initial and follow-up reporting of EIU cases. In the rare event that the Investigator's site does not become aware of the occurrence of a SAE immediately (e.g., if an outpatient study subject initially seeks treatment elsewhere), the Investigator's site is to report the event immediately after learning of it as described and document the time of the study site's first awareness of the adverse event.

For all SAEs, the Investigator is obligated to pursue and provide information to the Sponsor in accordance with the timeframes for reporting specified above. In addition, an Investigator may be requested by the Sponsor to obtain specific additional follow-up information in an expedited fashion. This information may be more detailed than that captured on the adverse event case report form. In general, this will include a description of the adverse event in sufficient detail to allow for a complete medical assessment of the case and independent determination of possible causality. Information on other possible causes of the event, such as concomitant medications and illnesses must be provided. In the case of a subject death, a summary of available autopsy findings (if available) and death certificate should be collected if permission is obtained from the subject's family. For a hospitalization, a copy of the hospital discharge summary should be requested. If obtained, these documents (with subject's personal identifiers redacted) should be submitted as soon as possible to the Sponsor or its designated representative.

Appropriate SAE forms will be provided to the study site at the initiation of the study. Upon notification of an SAE at the study site, the Investigator or designated study site staff should

call and speak to their Sponsor's study team contact immediately to initially notify them of the SAE.

Within 24 hours of awareness of the event, the Investigator or designated study site staff:

- complete the Clinical SAE Report Form ([provided by the Sponsor] with as much information as possible, however at a minimum, the subject identification number, name of product, SAE, and name of reporter are required);
- ensures the Investigator signs the Clinical SAE Report Form before sending to the Sponsor;
- scans and send via secure email the Clinical SAE Report Form to the Sponsor contacts.
-

13.15. Special Situations

This category of AEs is required for studies involving medicinal investigational products.

Special Situations (SS): Safety events that may not meet the definition of an AE; however, are required to be collected to meet Health Authority requirements. Examples include:

- Overdose of a J&J medicinal product
- Pregnancy exposure (maternal and paternal) to a J&J medicinal product
- Exposure to a J&J product from breastfeeding
- Suspected abuse/misuse of a J&J medicinal product
- Inadvertent or accidental exposure to a J&J medicinal product (including occupational exposure).
- Any failure of expected pharmacological action (i.e., lack of effect) of a J&J product.
- Unexpected therapeutic or clinical benefit from use of a J&J product.
- Medication error involving a J&J medicinal product with or without patient/consumer exposure to the J&J product, (e.g., product name confusion) OR that caused an unintended effect or could cause an intended effect (e.g. adult medicine given to a young child).
- Suspected transmission of an infectious agent via a J&J product.

**Wound Care Microbiome Study
Protocol: CO-170726100607-SACT
Amendment 2: 22JAN2018**

All nonserious adverse events are to be reported on the adverse event CRFs and will be submitted to the Sponsor.

14. STATISTICS

The Sponsor will be responsible for the data management and statistical analyses of this study. The skin microbiome [REDACTED] data will be analyzed and reported independently by external partners. The imaging data will be analyzed by the sponsor.
Sample Size Determination

The sample size of this exploratory study is not based on the statistical power consideration.

14.1. Analysis Populations

The efficacy analysis will be based on the Intent-to-treat (ITT) principle, i.e., all subjects who received induced wounds and started the bandage or no treatment will be included in the analysis.

The safety analysis will be based on all subjects who received induced wounds.

14.2. Efficacy Analysis

The analysis of the predominant microflora will be performed by Research and Testing Laboratories, LLC (external partner).

TEWL, [REDACTED] and DRS are measured at Baseline, Days 1-7 and Day 14. The triplicate values at each assessment time point will be averaged as the final response value, with the exception of the DRS which will have 5 replicates at each timepoint.

The final response values of TEWL and DRS will be summarized at each assessment time point by the assigned test products.

The within product comparison will be performed using the paired t-test to compare the values of each product at each post baseline time point with its own baseline value.

The between products comparison will be performed based on the change from baseline (post baseline value minus baseline value). The change from baseline of each product will be analyzed using mixed effect ANCOVA model at each post baseline time point. The ANCOVA model will include the product as the factor and the baseline value as the covariate. The model will include the subject as a random effect to incorporate the within subject correlation. The adjusted mean of each product from the ANCOVA model will be compared between the test products and the negative control, between the test products and the positive control, and between the negative control and the positive control.

[REDACTED]

14.3. Subjects Who Use Rescue Therapy or Discontinue

Subjects who use rescue therapy and are not withdrawn from the study will continue to be assessed per protocol and all data points will be included in the analysis. For subjects who discontinue(for any reason) the study early, data points already collected will be included in the analysis.

14.4. Safety Analysis

All subjects who receive at least one dose of study treatment will be included in the safety analysis. All adverse events reported during the adverse-event reporting period will be listed by subject number and treatment. The number of subjects experiencing adverse events will be presented by body system, preferred term, and treatment. The latest version of the Medical Dictionary for Regulatory Activities (MedDRA) will be used as the adverse event classification system.

15. DIRECT ACCESS TO SOURCE DATA/DOCUMENTS

The Investigator(s)/institution will permit study-related monitoring, audits, IRB/IEC review and regulatory inspection(s) by providing direct access to source data/documents.

15.1. Study Monitoring

Before an investigational site can enter a subject into the study, a representative of the Sponsor will visit the investigational study site to:

- Determine the adequacy of the facilities
- Discuss with the Investigator(s) and other personnel their responsibilities the site's responsibility with regard to protocol adherence as well as the study and monitoring responsibilities of the Sponsor or its representatives. These responsibilities will be documented in a written agreement between the Sponsor and the Investigator.

The site will be fully trained in the protocol during the Initiation visit or web-ex. During the study, a monitor from Sponsor or representative will have regular contacts with the investigational site, for the following:

- Provide information and support to the Investigator(s)
- Confirm that facilities remain acceptable
- Confirm that the investigational team is adhering to the protocol, that data are being accurately recorded in the CRFs, and that IP accountability checks are being performed
- Perform source data verification. This includes a comparison of the data in the CRF with the subject's medical records at the hospital or practice, and other records relevant to the study. This will require direct access to all original records for each subject (e.g., clinic charts).
- Record and report all protocol deviations not previously sent to Sponsor.
- Confirm AEs and SAEs have been properly documented on CRFs and confirm any SAEs have been forwarded to Sponsor and those SAEs that met criteria for reporting have been forwarded to the IRB/IEC.

The monitor will be available between visits if the Investigator(s) or other staff needs information or study-related direction.

15.2. Audits and Inspections

Authorized representative of Johnson & Johnson, a regulatory authority, an Independent Ethics Committee or an Institutional Review Board may visit the site to perform audits or inspections, including source data verification. The purpose of a Johnson & Johnson audit

or inspection is to systematically and independently examine all study-related activities and documents to determine whether these activities were conducted, and data were recorded, analyzed, and accurately reported according to the protocol. Good Clinical Practice guidelines of the International Conference on Harmonization, and any applicable regulatory requirements. The Investigator should contact their study contacts immediately if contacted by a regulatory agency about an inspection.

15.3. Institutional Review Board(IRB)

The Principal Investigator must obtain IRB approval for the investigation. Initial IRB approval, and all materials approved by the IRB for this study include subject consent form and recruitment materials must be maintained in the Site Master File by the Investigator and made available for inspection.

16. QUALITY CONTROL AND QUALITY ASSURANCE

Authorized representatives of the Sponsor, a regulatory authority, an IEC or an Institutional Review Board may visit the site to perform audits or inspections, including source data verification. The purpose of a Sponsor audit or inspection is to systematically and independently examine all study-related activities and documents to determine whether these activities were conducted, and data were recorded, analyzed, and accurately reported according to the protocol, GCP guidelines of the ICH E6, and any applicable regulatory requirements. The investigator should contact their study contacts immediately if contacted by a regulatory agency about an inspection.

17. DATA HANDLING AND RECORDKEEPING

17.1. Case Report Forms/Electronic Data Record

As used in this protocol, the term case report form (CRF) should be understood to refer to the Electronic Data Capture system.

The EDC system, is the database where pertinent study data is collected such as demography, subject randomization, adverse events, and subject disposition.

Electronic Data Capture pages should be completed for each randomized subject. The completed pages of the EDC system are the sole property of the Sponsor and should not be made available in any form to third parties, except for authorized representatives of the Sponsor or appropriate regulatory authorities, without written permission from the Sponsor.

All data will be collected on source documents first and the relevant data needed for analysis will be recorded in the Electronic Data Capture (EDC) system except DRS data. The DRS data will be reported into an macro-enabled audit trail Excel worksheet [REDACTED]

[REDACTED] be analyzed by external providers and this data will not be entered into the EDC system.

It is the Investigator's responsibility to ensure completion and to review and approve all information captured in the EDC. The subject's data in the EDC system must be electronically signed by the Investigator. These signatures serve to attest that the information contained in the EDC system is true. At all times, the Investigator has final personal responsibility for the accuracy and authenticity of all clinical data entered in the EDC. Subject source documents are the Investigator's subject records maintained at the study site. In cases where the source documents are the hospital or the physician's chart, the information collected in the EDC must match those charts.

All final data recorded in EDC system will be kept by the Sponsor and at the clinical site.

All data recorded on source documents will be kept at the clinical site.

17.2. Inspection of Records

To enable evaluations and/or audits from regulatory authorities or the Sponsor, the investigator agrees to keep records including the identity of all participating subjects (sufficient information to link records, e.g., CRFs and hospital records), all original signed informed consent forms, copies of all CRFs, SAE forms, source documents, and detailed records of treatment disposition. The records should be retained by the investigator according to ICH guidelines, local regulations, or as specified in the Clinical Study Agreement, whichever is longer.

17.3. Retention of Records

The Principal Investigator must maintain all documentation relating to the study for a period of 2 years after the last marketing application approval, or if not approved 2 years following the discontinuance of the test article for investigation. If it becomes necessary for Johnson & Johnson or the Regulatory Authority to review any documentation relating to the study, the Investigator must permit access to such records.

If the investigator relocates, retires, or for any reason withdraws from the study, the Sponsor should be prospectively notified. The study records must be transferred to an acceptable designee, such as another investigator, another institution, or to the Sponsor. The investigator must obtain Sponsor's written permission before disposing of any records, even if retention requirements have been met.

18. SPONSOR DISCONTINUATION CRITERIA

Premature termination of this clinical study may occur because of a regulatory authority decision, change in opinion of the IRB/EC, drug safety problems, or at the discretion of the sponsor. In addition, the Sponsor retains the right to discontinue the study at any time.

If a study is prematurely terminated or discontinued, the Sponsor will promptly notify the investigator. After notification, the investigator must contact all participating subjects within a time period set by the Sponsor (usually two weeks). All study materials must be collected and all CRFs completed to the greatest extent possible.

19. PUBLICATION POLICY

Publication of study results by the Investigator is discussed in the Clinical Study Agreement, as appropriate. Results from this study may be published in the form of oral or written presentations at scientific meetings or as one or more peer-reviewed journal articles. In these cases, no information on individual subjects will be revealed.

APPENDIX 1 INSTRUCTIONS FOR USE – TEST SITES

SITE LOCATION AND SELECTION:

VIEW OF SUBJECT'S BACK

HEAD

LEFT SIDE

RIGHT SIDE

Bra Line for Females

Site 1	Spine	Site 2
Site 3		Site 4
Site 5		Site 6

1 INTRODUCTION

The skin is colonized by diverse microorganisms, and the genetic contributions of these microorganisms is collectively referred to as the skin microbiome. These microorganisms, in combination with mammalian cells of the host produce a diverse array of metabolites, which are unique chemical fingerprints left behind by specific cellular processes, important for normal cell function. The microorganisms and metabolic processes exist in a dynamic equilibrium and are believed to contribute to acute wound healing. However, when the skin is compromised (i.e. a wound occurs), adverse organisms can also colonize and metabolite profiles can shift in the wound leading to impaired or prolonged healing 1,2. Thus, characterizing the skin microbiome and metabolites during the wound healing process is critical to understanding their role in wound repair.

This exploratory study is being conducted to characterize the microbial load and diversity of the skin microbiome and metabolites of induced wounds in relation to specific skin properties, and after treatment with various adhesive bandages to further establish the role of microorganisms in wound healing.

1.1 Study Objectives

The primary objective of this study is to evaluate skin microbiome changes of induced wounds covered with adhesive bandages in comparison to uncovered wounds and intact skin in healthy subjects.

The secondary objective of this study is to evaluate the following for induced wounds covered with adhesive bandages in comparison to uncovered wounds and intact skin: changes in skin barrier function, and skin redness. [REDACTED]

[REDACTED]

1.2 Study Design

This single center, 15-day clinical trial is being conducted to assess the changes to the skin microbiome of induced wounds on the backs of approximately 35 healthy adult subjects aged 18-55 years, with Fitzpatrick Skin Types I – III. There will be 6 test sites randomly assigned to treatments for each subject. Four of the test sites will be wounded and covered with various marketed adhesive bandages, one test site will be wounded and un-covered (positive control) and one test site will remain intact and un-covered (negative control). Following a screening visit (Day -3 to -14) and a 3-day washout period, subjects will be assessed at Baseline (Day 0), Days 1 – 7 and Day 14; subjects will also return to the study site daily for bandage changes.:

The following assessments will be performed by trained study staff at Baseline (Day 0), Days 1-7, and Day 14:

- Microbiome [REDACTED] Swabs will be used to collect bacteria [REDACTED] from the skin surface. A total of 2 swabs will be taken per site per timepoint.
- Trans Epidermal Water Loss (TEWL; tewameter): Noninvasively measures water evaporation from the skin, which is a measure of skin barrier function. These measurements will be done three times for each test site.
- [REDACTED]
- Skin pH (Skin pH Meter PH905): Noninvasively measures skin surface pH. [REDACTED]
- Diffuse Reflectance Spectroscopy (DRS): Noninvasively measures redness by oxy-, deoxy-hemoglobin, and melanin levels in the skin. Five repetitive spectra acquisition will be implemented for each test site.
- [REDACTED].

A randomization code will designate which test site will receive the appropriate treatment. A subgroup of 17 subjects will also be randomly assigned for additional metabolite analysis. Study bandages will be changed daily (by study staff on each day of the study Days 1 -14). Subjects will report back to the study facility for daily bandage changes (Days 1-14) and for assessments on Days 1-7 and 14.

Adverse events will be monitored throughout the study.

2 INTERIM ANALYSES

No interim analysis is planned for this trial.

3 ANALYSIS SETS

3.1 Primary Analyses Set

The efficacy analysis will be based on the Intent-to-treat (ITT) principle, i.e., all subjects who received induced wounds and started the bandage or no treatment will be included in the analysis.

3.2 Per-Protocol Set

Not applicable.

3.3 Safety Analysis Set

The safety analysis will be based on all subjects who received induced wounds.

4 EFFICACY ASSESSMENTS AND ENDPOINTS

4.1 Efficacy Assessments

- Predominant microflora based on the following criteria:
 - Microbial Community Richness on the back at Baseline (Day 0), Days 1-7, and Day 14, based on the total number of different bacterial taxa detected in the sample.
 - Microbial Community Diversity on the back at Baseline (Day 0), Days 1-7, and Day 14 based on the Shannon Index.
 - Microbial Community Evenness on the back at Baseline (Day 0), Days 1-7, and Day 14 based on Pielou's evenness index.
- Skin barrier function as assessed by mean TEWL measurements of all test sites at Baseline (Day 0), Days 1-7 and Day 14.
- Redness as assessed by mean DRS measurements of oxy-, deoxy-hemoglobin, and melanin levels at all test sites at Baseline (Day 0), Days 1-7 and Day 14.
- [REDACTED]
 - [REDACTED]
 - [REDACTED]
 - [REDACTED]
 - [REDACTED]

4.2 Efficacy Endpoints

[REDACTED]

The following efficacy endpoints will be analyzed by the statistical group of J&J Consumer Group.

- Change from baseline in TEWL measurements at Days 1-7 and Day 14.
- Change from baseline in DRS measurements at Days 1-7 and Day 14.
- [REDACTED]
- Change from baseline in Skin pH at Days 1-7 and Day 14.

4.3 Safety Assessments and Endpoints

Safety assessments consist of Adverse Events.

- Number and percentage of subjects with treatment-emergent adverse event
- Number and percentage of subjects with treatment-related adverse event
- Number and percentage of subjects with serious adverse event

4.4 Other Endpoints

Not applicable.

4.5 Covariates

For the analyses of Change from Baseline in TEWL, [REDACTED], skin pH and DRS measurement, corresponding baseline value will be adjusted in the models as covariate.

5 HANDLING OF MISSING VALUES

No imputation of missing data will be performed.

6 STATISTICAL METHODOLOGY AND STATISTICAL ANALYSES

6.1 Statistical Hypotheses

For each between-product comparison, the null hypothesis that the product mean change from baseline are equal will be tested against the alternative hypothesis that the product mean change from baseline are not equal.

In other words, the following hypothesis will be tested:

$$H_0: \mu_1 = \mu_2$$

against the two-sided alternative

$$H_1: \mu_1 \neq \mu_2$$

where μ_1 and μ_2 are the mean change from baseline for the two product groups, respectively.

6.2 Statistical Decision Rules

The comparison between products will be performed at the 0.05 level of significance, two-sided and all analyses are exploratory. Thus, for any given comparison, the null hypothesis of no difference in treatment means will be rejected if, and only if, the corresponding test p-value is equal to or smaller than 0.05.

6.3 Statistical Methods

TEWL, ~~SKICON~~, skin pH and DRS are measured at Baseline, Days 1-7 and Day 14. The triplicate values at each assessment time point will be averaged as the final response value, with the exception of the DRS which will have 5 replicates at each timepoint.

The final response values of TEWL, DRS, SKICON and skin pH will be summarized at each assessment time point by the assigned test products.

The within product comparison will be performed using the paired t-test to compare the values of each product at each post baseline time point with its own baseline value.

The between products comparison will be performed based on the change from baseline (post baseline value minus baseline value). The change from baseline of each product will be analyzed using mixed effect ANCOVA model at each post baseline time point. The ANCOVA model will include the product as the factor and the baseline value as the covariate. The model will include the subject as a random effect to incorporate the within subject correlation. The adjusted mean of each product from the ANCOVA model will be compared between the test products and the negative control, between the test products and the positive control, and between the negative control and the positive control.

The mixed effect analysis of covariance model can be performed by the following SAS codes

```
PROC MIXED DATA = <dataset>;
  CLASS subjID treatment;
  MODEL chg = treatment baseline/solution ddfm = contain;
  RANDOM subjID ;
  LSMEANS treatment/diff cl;
  ESTIMATE "Positive Control vs. Negative Control" treatment -1 1 0 0 0 0 /cl;
  ESTIMATE "Product #1 vs. Negative Control" treatment -1 0 1 0 0 0 /cl;
  ...
  RUN;
```

Note:

1. Assume Negative Control = “A”, Positive Control = “B”, Product #1 = “C”, Product #2 = “D”, Product #3 = “E”, Product #4 = “F”.

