- Six test sites will be identified on the back.
- 5 test sites will be wounded using a tape-stripping method as described in Section 11.8, five uniform wounds will be created by the trained study staff on the subjects back according to the randomization schedule.
- Four of the test sites will be wounded and covered with various marketed adhesive bandages (treatment groups); one test site will be wounded and un-covered (positive control) and one test site will remain intact and un-covered (negative control).
- The following assessments will completed on each test site, in the order below:
 - [REDACTED]
 - Trans Epidermal Water Loss (TEWL; tewameter): Noninvasively measures water evaporation from the skin, which is a measure of skin barrier function. These measurements will be done three times for each test site.
[REDACTED]
 - [REDACTED]
 - Diffuse Reflectance Spectroscopy (DRS): Noninvasively measures redness by oxy-, deoxy-hemoglobin, and melanin levels in the skin. Five repetitive spectra acquisition will be implemented for each test site.
 - Microbiome [REDACTED] sampling: Swabs will be used to collect bacteria [REDACTED] from the test site surface. A total of 2 swabs will be taken per test site, plus control swabs.
- Bandages will be placed on the wounds according to the randomization schedule.
- Subjects will be provided written and verbal instructions.
- Subjects will be informed of their next appointment.

- Subjects will report back to the study facility for daily bandage changes (Days 1-14) and for assessments on Days 1-7 and 14. All clinic visits will be at approximately the same time.

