11.8.1. Site Selection

Six test sites will be identified by the investigative staff and numbered from 1 to 6. The selected sites will be free from nevi or other skin conditions. Using a template and permanent marker, six (6) test areas will be marked at least 2" – 3" apart from each other

on the back on each subject. Test sites will be positioned side by side on a rectangular design so that three are made on each side of the spine. The test sites will be located paraspinally with three test sites on each side of the mid back below the shoulder blades.. Enough space will be left between the test sites so that the bandages can be placed over the wounds without an overlap. If the subject is female, the test sites will be positioned below the bra line.

The randomization schedule will detail the treatment assignments for each test site. Tape Stripping Procedure & Preparation

- The subjects will rest in a prone position (front or ventral surface downward) for the wounding procedure. Instruments used will be sterile. The Investigator or trained clinician creating the wounds as well as assisting staff will wear gloves. Test sites may be re-marked as needed.
- All test sites will be cleaned with an alcohol wipe prior to wounding. NOTE: the test site randomly assigned to be intact (unwounded) and untreated will not be wiped with alcohol.
- Superficial irritation will be created by a tape stripping method to obtain a glistening layer using 3M tape or similar ,(3M St. Paul, MN, USA) for sequential stripping of the epidermis of the test site.
- Strips may be pre-cut and placed on release paper.
- Approximately a 1 cm x 1 cm wound will be created on each of the designated test sites.
- The technician will place the tape on the test site, press it down, rub firmly within the test site marks, and remove the strip with a strong and quick stroke.
- This process will be repeated until a clear glistening layer will be visualized upon removal of the strip. The number of stripplings necessary to reach the glistening layer varies among subjects and depends upon the thickness and looseness of the subject's stratum corneum layer.
- The number of strips used per site will be recorded in the source document.

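### If Day 0 readings follow wounding, as the Visit 2 step order suggests, the SAP 6.3 baseline covariate moves the five contrasts with intact skin off the SAP 6.1 hypothesis

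*SAP*

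**What the plan says.** **Analysis.** SAP 6.1 sets the hypothesis for every between-product comparison: "the null hypothesis that the product mean change from baseline are equal will be tested". SAP 6.3 then fits, at each post-baseline day, a mixed model for change from baseline: "The ANCOVA model will include the product as the factor and the baseline value as the covariate". The code is "MODEL chg = treatment baseline/solution ddfm = contain", with a random subject effect. It has one baseline slope for all six conditions and no treatment-by-baseline term. Protocol 14.2 describes the same model. The planned contrasts are four products against the negative control, four products against the positive control, and one control against the other.

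**Levels.** SAP 6.3 also says: "The final response values of TEWL, DRS, SKICON and skin pH will be summarized at each assessment time point by the assigned test products". In the visible text this is descriptive only. No test or interval for wound level against intact-skin level is planned.

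**Visit 2.** Protocol 11.2 lists, in this sequence:
- "5 test sites will be wounded using a tape-stripping method as described in Section 11.8"
- "The following assessments will completed on each test site, in the order below"
- "Bandages will be placed on the wounds according to the randomization schedule"

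The negative control is not wounded, and Protocol 11.8.1 adds that "the test site randomly assigned to be intact (unwounded) and untreated will not be wiped with alcohol".

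**Objective.** The secondary objective (Protocol 8) compares covered wounds with uncovered wounds and with intact skin, on changes in barrier function and redness.

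**The concern.** Baseline adjustment in a randomised comparison relies on the baseline being untouched by the assignment, so that expected baselines are equal. Here the randomisation decides which sites are wounded. If Day 0 is read after wounding, it is a fresh-wound value at five sites and an untouched-skin value at the sixth, and the covariate has itself been changed by the assignment. A common slope then carries the Day 0 gap into every contrast with intact skin.

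At stake is the comparison with intact skin, which is half of the secondary objective. Five of the nine contrasts on eight post-baseline days are exposed: 5 x 8 = 40 of 9 x 8 = 72 tests per measure. The shift is zero wherever the slope or the gap is zero. A half-healed wound could be reported as nearly equal to intact skin, or equal changes could be declared different.

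**Working it through.** **1. Timing.** The evidence that Day 0 readings follow wounding:
- Protocol 11.2 lists wounding, then assessments, then bandaging.
- Protocol 11.3 and 11.5 refer back to the Visit 2 measurements as assessments of wounds.
- Protocol 12.1.5 plans the DRS acquisitions on wound sites at every time point.
- Protocol Table 1 lists wounding above swabs, TEWL and DRS.
- No pre-wounding reading is described at Visit 2.

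No sentence states the order, so this remains an inference.

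**2. What the model estimates.** Let D_post and D_0 be the wound-minus-intact differences in mean at the visit and at Day 0. Let b be the common slope of change on Day 0 value, and b_post = 1 + b the slope of post value on Day 0 value.

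Adjusted contrast = (D_post - D_0) - b x D_0 = D_post - b_post x D_0.

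- It equals the mean-change difference D_post - D_0 only if b_post = 1 (or D_0 = 0).
- It equals the level difference D_post only if b_post = 0 or D_0 = 0.
- Among the five wounded sites the expected D_0 is 0 by randomisation, so the problem does not arise there.

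**3. Inputs for size.** The documents give no TEWL values, SDs or power figure, so there is no planned figure to reproduce. Assumed:
- Intact skin 8 g/m2h; Day 0 gap 32; reading noise SD 1.5; intact between-subject SD 1.5.
- 35 subjects x 6 sites.
- Four splits of wound-depth SD between subjects / between sites: 5/5, 6.4/3, 8/3 and 3/6.4.
- Residual wound fully, half or not tied to Day 0 depth.

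The SAP model was fitted by REML with containment df 210 - 35 - 5 - 1 = 169, in 1000 simulated trials per setting.

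**4. Formula check** (half healed, 5/5 split, b_post 0.483 / 0.246 / 0.015):
- 16 - 0.483 x 32 = 0.54; simulated 0.56
- 16 - 0.246 x 32 = 8.13; simulated 8.10
- 16 - 0.015 x 32 = 15.52; simulated 15.54

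**5. Results** (fully / half / not tied; ranges over the four splits):

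| Wound at the visit | Level difference | Change difference | Planned estimate | Consequence |
|---|---|---|---|---|
| Unhealed | 32 | 32 - 32 = 0 | 1.2-1.8 / 16.5-17.5 / 31.1-31.7 | True SAP 6.1 null rejected 36-53% / 100% / 100% |
| Half healed | 16 | 16 - 32 = -16 | 0.45-0.66 / 7.97-8.36 / 15.3-15.7 | 95% CI contains level difference 0% / 0% / 83-92%, change difference 0% |
| Fully healed | 0 | 0 - 32 = -32 | -0.3 to -0.6 | Zero rejected 7-10% |

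With a gap of 20, half healed (level difference 10; 5/5 split), the estimates are 0.35 / 5.1 / 9.7.

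**6. Different assumptions** (wounded Day 0 mean 50, intact 10, gap 40, 30 subjects for rejection rates):
- Level difference 15, change difference -25. Slopes 0.2, 0.5 and 0.8 give 15 - 8 = 7, 15 - 20 = -5 and 15 - 32 = -17; simulated 7.0, -5.1 and -17.0.
- Mean changes equal: 32.0, 20.1 and 8.0, with the true null rejected in 100%, 100% and 98% of trials.
- Mean changes equal, gap only 10: 7.9, 5.1 and 2.1, rejected in 100%, 97% and 30%.

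**7. Where the problem is absent.**
- Product against positive control (true difference 0; step 3 assumptions, gaps 32 and 20): estimates -0.03 to 0.10, rejection 3.6-6.8%.
- Day 0 read before wounding: estimate 16.0 against 16, 94% coverage, 5.2% false rejection when healed.

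**The case against.** **Timing is not proven.** This stands. The bullet saying that four sites are wounded and covered also precedes the assessments, although bandages go on afterwards, so the list is not a strict clock. Table 1 is not one either: it places swabs above TEWL, while 11.2 lists sampling last. The instruction on order governs only the sequence among the assessments, and step-by-step equipment instructions sit in a separate document (Protocol 12). A reader might infer that the protocol states post-wounding readings; it does not.

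**Table 1 shows a TEWL mark at Screening.** A reader might infer a pre-wound baseline from it. The documents do not support that: 11.1 lists no screening TEWL, 12.1.2 gives Days 0, 1-7 and 14, and baseline is Day 0.

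**The contrast is sometimes close to the level difference.** This stands. A reader might infer that the contrasts always estimate neither quantity. With residual wound not tied to Day 0 depth, the estimate is 15.3-15.7 against 16, and near full healing the shift is small under the assumed healing model.

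**Not all undercoverage is due to the covariate.** This stands for the not-tied case. At the 8/3 split, a repeat simulation gave 78% coverage with a shift of only about 0.2. A random-intercept model on levels with no covariate covered 86.1% at that split (unhealed). Unequal variances therefore contribute.

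**The endpoint is change, so a level analysis is a preference.** This stands in part. SAP 4.2 and 6.1 and the objective speak of change, and an unadjusted change contrast would honour them. The planned adjusted contrast does not.

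**A reader can rebuild the level difference.** Only as a point estimate: levels are summarised and the code prints the slope, but the planned interval and p-value would still address something else.

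**Conclusion.** The concern holds conditionally. If Day 0 readings follow wounding, which the documents indicate but do not state, the five contrasts with the negative control equal the level difference minus b_post times the Day 0 gap. Between the limiting slopes this is neither the SAP 6.1 mean-change difference nor the level difference, and a true SAP 6.1 null can be rejected far more often than 5%.

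The identity is algebra. The size rests wholly on assumed TEWL values; DRS and skin pH were not simulated, and any measure with a small Day 0 gap has a small shift. If wounded and intact Day 0 readings barely overlap, the adjusted contrast also rests on extrapolating the common slope.

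A reader might infer that the whole between-product analysis is unsound. It is not: product-versus-positive-control contrasts are essentially unaffected, and the primary microbiome analysis is done separately by external partners. SAP 6.2 labels all analyses exploratory, so the harm is a misread comparison with intact skin, not a false confirmatory claim. It should be fixed before analysis. Confidence is medium because the timing is inferred.

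**What to change.** **(a)** State in Protocol 11.2 and SAP 6.3 whether the Day 0 readings precede or follow wounding. If they precede it, nothing else changes.

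**(b)** If they follow it, remove the Day 0 covariate from the five contrasts with the negative control. Use within-subject paired differences (each site minus that subject's intact site) with a paired t interval:
- Paired change from baseline keeps SAP 6.1 and 4.2 as written. Simulated coverage was 94-97%.
- Add the paired post-baseline level difference, labelled as such, to show how far the wound still is from intact skin. Simulated coverage was 94.4-95.6%. A single random intercept on levels is not a substitute: it covered 85.0-98.1%.

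Keep the planned ANCOVA for test products against the positive control.

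**Matching edits:** the statistical methods in the Protocol synopsis, Protocol 14.2 and SAP 4.5; also SAP 4.2 and the titles of Tables 14.2.1-14.2.4 if the level difference is added.

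**Cost:** no new data, and one extra analysis per endpoint and day. The five contrasts lose the covariate. Under the assumed TEWL values, the paired 95% half-width for the level difference with 35 subjects is 2.5-3.0 unhealed, 1.4-1.6 half healed and 0.7-0.8 at 90% healed or more. With 30 subjects the first two become 2.7-3.3 and 1.5-1.8.
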